16.1.3.2 Inadequate use of ICS

As a part of main analysis, inadequate use of ICS will be presented as in the previous section 16.1.3.1. Current treatment with ICS. This analysis will be presented only for patients without exacerbations in the previous year. This cohort will be used because only patients without exacerbations can receive ICS without requiring it, which is, making an inappropriate use of the treatment.

Document: \\bcnfs02\general\Hdmgener\MEDICAL AFFAIRS 28.02.2017 actualizada\8. SRO ESTUDIOS\RESPIRATORIO\1237-0070 NIS OPT\11 - Clinical Trial Report\SAP\SAP - V 1.0\SAP OPTI version1.0 29052019.docx

Author:

Version Number: 1.0

Version Date: [29MAY2019]

Template No.: RWI_TP_BIOS0013 Revision 1

Reference: RWI_WI_BIOS0015

Effective Date: 15Jun2018

Copyright © 2018 All rights reserved. The contents of this document are confidential and proprietary to Holdings Inc. and its subsidiaries. Unauthorized use, disclosure or reproduction is strictly prohibited.

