7.2.11 Risk stratification

Patients will be classified according to their risk based on GesEPOC 2017 Spanish guideline:

- Low risk:
 - FEV₁(%) post-bronchodilation ≥ 50% and,
 - mMRC 0-2, and
 - 0 or 1 exacerbation in the last year, and
 - without hospitalization in the last year.
- High risk:
 - FEV₁(%) post-bronchodilation <50% or,
 - mMRC > 2 or mMRC = 2 with treatment or,
 - 2 or more exacerbation in the last year or,
 - 1 or more exacerbation with hospitalization in the last year.

Document: \\bcnfs02\general\Hdmgener\MEDICAL AFFAIRS 28.02.2017 actualizada\8. SRO ESTUDIOS\RESPIRATORIO\1237-0070 NIS OPTI\11 - Clinical Trial Report\SAP\SAP - V 1.0\SAP OPTI version1.0 29052019.docx

Author: Version Number: 1.0

Version Date: [29MAY2019]

Template No.: RWI_TP_BIOS0013 Revision 1

Reference: RWI_WI_BIOS0015

Effective Date: 15Jun2018

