Phenotype, obtained from Figure 4 in “Guía española de la enfermedad pulmonar obstructiva crónica (GesEPOC) 2017. Tratamiento farmacológico en fase estable” in

<http://www.archbronconeumol.org/es-pdf-S0300289617300844>.

Document: \\bcnfs02\general\Hdmgener\MEDICAL AFFAIRS 28.02.2017 actualizada\8. SRO ESTUDIOS\RESPIRATORIO\1237-0070 NIS OPTI\11 - Clinical Trial Report\SAP\SAP - V 1.0\SAP OPTI version1.0 29052019.docx

Author: Version Number: 1.0
Version Date: [29MAY2019]

[figure not shown]
Template No.: RWI_TP_BIOS0013 Revision 1 Reference: RWI_WI_BIOS0015

Effective Date: 15Jun2018

The use of ICS is indicated only in these cases:

- Patients at high risk and,
 - Phenotypes: exacerbator with emphysema, exacerbator with chronic bronchitis or mixed COPD - asthma syndrome (ACOS). Only mixed phenotype allows the use of ICS as the first option. For exacerbator with chronic bronchitis and exacerbator with emphysema, the use of ICS is indicated after a first treatment of LAMA / LABA, when there is worsening of symptoms.

Table D: Treatment COPD scheme according to risk and phenotype

Document: \\bcnfs02\general\Hdmgener\MEDICAL AFFAIRS 28.02.2017 actualizada\8. SRO ESTUDIOS\RESPIRATORIO\1237-0070 NIS OPTI\11 - Clinical Trial Report\SAP\SAP - V 1.0\SAP OPTI version1.0 29052019.docx

Author:

Version Number: 1.0

Version Date: [29MAY2019]

Template No.: RWI_TP_BIOS0013 Revision 1

Reference: RWI_WI_BIOS0015

Effective Date: 15Jun2018

Copyright © 2018 All rights reserved. The contents of this document are confidential and proprietary to subsidiaries. Unauthorized use, disclosure or reproduction is strictly prohibited.

Holdings Inc. and its

[figure not shown]

Figure 4 in “Guía española de la enfermedad pulmonar obstructiva crónica (GesEPOC) 2017. Tratamiento farmacológico en fase estable” (<http://www.archbronconeumol.org/es-pdf-S0300289617300844>)

Taking into account the algorithm of treatment recommendations included in GesEPOC (phenotype) guidelines, we will define patients as:

- Adherent to ICS (Adequate use of ICS):
 - Patients treated with ICS that according to GesEPOC guidelines should have been treated with ICS, or
 - Patients **not** treated with ICS that according to GesEPOC guidelines should **not** have been treated with ICS.
- Non-Adherent to ICS (Inadequate use of ICS):
 - Patients treated with ICS but according to GesEPOC guidelines should **not** have been treated with ICS, or

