 - Patients **not** treated with ICS but according to GesEPOC guidelines should have been treated with ICS.

Document: \\bcnfs02\general\Hdmgener\MEDICAL AFFAIRS 28.02.2017 actualizada\8. SRO ESTUDIOS\RESPIRATORIO\1237-0070 NIS OPTI\11 - Clinical Trial Report\SAP\SAP - V 1.0\SAP OPTI version1.0 29052019.docx

Author:

Version Number: 1.0

Version Date: [29MAY2019]

Template No.: RWI_TP_BIOS0013 Revision 1

Reference: RWI_WI_BIOS0015

Effective Date: 15Jun2018

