20. TABLES AND FIGURES

20.1 Evaluability

Table 3. Evaluability criteria – Patients in the FAS

		Total
Total included patients (ENR)		
Evaluable patients	Evaluable patients (FAS)	
	Non-Evaluable patients	
Reasons for non-evaluable patients	Inclusion criteria 1	
	Inclusion criteria 2	

ICS Analysis Set (PICAS)		
Safety Analysis Set-ICS		
Safety Analysis Set- BI drug		

Table 4. Other protocol violations occurred in evaluable patients

		Total
Evaluable patients	Evaluable patients (FAS)	
Important protocol violations	ADR (serious or non-serious) or fatal event not notified to BI	
	Any other major or critical Non-Compliance detected during monitoring visit	

Table 5. Main stratification variables

		Total
Total evaluable (FAS)		
Current treatment on ICS	Total	
	No (Non - ICS treatment)	
	Yes (ICS treatment)	
	95% CI for current ICS treatment	
Moderate/severe exacerbations in the previous year	Total	
	No (Without Moderate/severe Exacerbations)	
	Yes (With Moderate/severe Exacerbations)	
	95% CI for presence of moderate/severe exacerbations in the previous year	
Inadequate use of ICS	Total	
	Adherent patients: Adequate use of ICS	

Document: \\bcnfs02\general\Hdmgener\MEDICAL AFFAIRS 28.02.2017 actualizada\8. SRO ESTUDIOS\RESPIRATORIO\1237-0070 NIS OPTI\11 - Clinical Trial Report\SAP\SAP - V 1.0\SAP OPTI version1.0 29052019.docx

Author:

Version Number: 1.0

Version Date: [29MAY2019]

Template No.: RWI_TP_BIOS0013 Revision 1

Reference: RWI_WI_BIOS0015

Effective Date: 15Jun2018

Copyright © 2018 All rights reserved. The contents of this document are confidential and proprietary to Holdings Inc. and its subsidiaries. Unauthorized use, disclosure or reproduction is strictly prohibited.

		Total
	Non-adherent patients: Inadequate use of ICS (use of ICS in patients without moderate/severe exacerbations in the previous year) 95% CI for non-adherent patients (inadequate use of ICS)	

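### The SAP applies the label non-adherent / inadequate use of ICS to two rules that classify some patients oppositely, and its passages on the cohort for the second rule conflict

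*SAP*

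**What the plan says.** **GesEPOC rule.** SAP 7.2.14 heads one class of patients "Non-Adherent to ICS (Inadequate use of ICS" (closing bracket omitted). It has two parts: patients given ICS whom the guideline would not treat, and patients not "treated with ICS but according to GesEPOC guidelines should have been treated with ICS" (in the source a bold *not* stands directly before the quoted words). Table 38 and protocol 9.3.2.2(h) use the same two-sided definition. Under 7.2.14, ICS is indicated only at high risk and only for the mixed or the two exacerbator phenotypes; "Only mixed phenotype allows the use of ICS as the first option". Risk comes from 7.2.11. Its low-risk list, which also needs FEV1, dyspnoea and no hospitalisation to fit, contains the line "0 or 1 exacerbation in the last year, and". Its high-risk criteria are alternatives, so FEV1 or dyspnoea alone can make a patient high risk.

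**Exacerbation rule.** Table 5 in SAP 20.1 has the row "Non-adherent patients: Inadequate use of ICS (use of ICS in patients without moderate/severe exacerbations in the previous year". Tables 25-27 carry the same definition in their titles and call it inadequate use, without adherence words. SAP 16.1.3.2 gives the reason, "only patients without exacerbations can receive ICS without requiring it", and the cohort: "This analysis will be presented only for patients without exacerbations in the previous year".

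**Other passages.** SAP 16.1.3 puts the primary analysis on the FAS, and the first row of Table 5 is "Total evaluable (FAS". Table 25 prints an undefined n/N and has previous-year moderate/severe and severe exacerbation rows running up to 5+. SAP 16.1.3.1 takes inadequate ICS use (yes/no) as the regression response without saying which rule is meant. Protocol 9.7.2 mentions inadequate use as an example of a regression outcome and does not define it.

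**The concern.** Adherence to GesEPOC is a protocol secondary outcome. If the report follows the SAP as written, Table 5 prints a non-adherent percentage that is not the protocol's measure, and Table 38 prints another that is. A patient can be adherent in one and non-adherent in the other, with nothing in the SAP to say that these are two measures. Predictors in Tables 25-27 could then be taken as predictors of departure from the guideline, which the exacerbation rule does not measure.

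The second problem is the base for the exacerbation rule. The percentage and its interval depend on whether exacerbators are in the denominator, and the passages point both ways. The same choice decides who is counted in the *Adherent* row of Table 5, and what happens to the Table 25 rows for previous-year exacerbations.

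**Working it through.** **1. Classify patients under both rules, using only SAP 7.2.11, 7.2.14 and Table 5.**

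| Patient | GesEPOC rule | Exacerbation rule |
|---|---|---|
| On ICS, mixed phenotype, high risk through FEV1 or dyspnoea, no exacerbation in the year | Adequate | Inadequate |
| Not on ICS, GesEPOC indication present (for example high-risk mixed phenotype) | Inadequate | Never inadequate |
| On ICS, low risk, one moderate exacerbation without hospitalisation | Inadequate | Not inadequate |

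The third row is a patient with an exacerbation who receives ICS without an indication under 7.2.14. The premise in 16.1.3.2 says there is no such patient. Other disagreements exist, but they depend on the charted phenotype or on the earlier bronchodilator step; these three are enough.

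**2. Reproduce the plan's own figure.** Inputs from protocol 9.5 and SAP 4.2: N = 900, 40%, Wald interval, 10% dropout.
- 1.96 × √(0.40 × 0.60 / 900) = 0.032, so 36.8% to 43.2%, as stated.
- 900 / (1 − 0.10) = 1,000, as stated.

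**3. Apply the two candidate denominators.** Further inputs from the same sections: 66% non-exacerbators, 61% of them on ICS. I take non-exacerbator to mean no moderate/severe exacerbation in the prior year, as the plan's calculation does.
- Non-exacerbators: 0.66 × 900 = 594. Exacerbators: 900 − 594 = 306.
- On ICS without exacerbation: 0.61 × 594 = 362.3.
- FAS: 0.66 × 0.61 = 40.26%; 1.96 × √(0.4026 × 0.5974 / 900) = 3.20 points; 95% CI 37.1% to 43.5%.
- Non-exacerbators: 362.3 / 594 = 61.0%; 1.96 × √(0.61 × 0.39 / 594) = 3.92 points; 95% CI 57.1% to 64.9%.

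The second figure is also the *No* column percentage for ICS users in Table 24, so on that cohort the measure repeats a cell already reported.

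**4. Who fills the *Adherent* row of Table 5.**
- On the FAS: 900 − 362 = 538, made up of all 306 exacerbators, whatever their GesEPOC status, plus 232 untreated non-exacerbators.
- On the 16.1.3.2 cohort: 594 − 362 = 232, with no exacerbators in the row.

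**5. Table 25 rows that are part of the response.** A patient with any previous-year moderate/severe exacerbation cannot be a *yes* under the exacerbation rule.
- On the FAS, every category above *None* in the moderate/severe and severe rows has zero events. Collapsed to two levels, 362/594 against 0/306 gives an odds ratio of 0, and the log odds ratio has no finite estimate, so the Wald limits and the p<0.1 screen mean nothing for that row.
- In the 16.1.3.2 cohort those categories are empty.

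On neither reading is the row informative.

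**The case against.** The best defence is that the exacerbation rule is written out in full wherever it is used. Tables 25-27 state it in their titles, and SAP 9 makes the tables the specification of the outputs, so the regression response can be identified. Only Table 5 attaches adherence words to it. The rule reflects the state that the protocol's primary outcome describes, and p-values are descriptive (SAP 8.2). All of this stands and limits the damage, but it does not remove the shared label in 7.2.14 and Table 5, or the conflict over the premise.

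Several stronger readings are tempting and are not supported:

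- *The cohort is missing.* SAP 16.1.3.2 names one. The fault is that other passages disagree with it. The *Inadequate use* block of Table 5 also has its own total row, which could hold a smaller denominator.
- *Patients with mild exacerbations are left in limbo.* SAP 16.1.3.2 gives no severity, and 7.2.6.1 counts mild events, but that section concerns total exacerbations. SAP 16.1.3.1 and the table titles say moderate/severe, and protocol 9.3.2.2 defines only those two grades. One added word settles it.
- *Every previous-year exacerbation covariate is part of the response.* An all-severity count is not strictly so, because a patient with mild events only can still be a *yes*. The point holds for the moderate/severe and severe rows.
- *Type of ICS is a faulty model term.* In Table 25 it has no reference level, and it is not in the 16.1.3.1 covariate list. It may be descriptive only.
- *The regressions will fail through separation.* That follows only if the FAS is used.

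**Conclusion.** The point holds as a labelling and specification fault that should be fixed before analysis. One label covers two rules, at least three kinds of patient are classified oppositely, and the premise in SAP 16.1.3.2 cannot stand beside 7.2.11 and 7.2.14 as they are written. The cohort passages must be reconciled. On planning inputs the choice of denominator moves the same 362 or so patients from 40.3% to 61.0%, with intervals that do not overlap.

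A reader might take that gap as the size of the disagreement between the rules. It is not. It shows the denominator effect alone and rests on the 66% and 61% planning rates at N = 900. The documents give no joint distribution of risk, phenotype and ICS use, so the number of patients classified oppositely cannot be computed. Nor is the primary result in doubt: Tables 24 and 38 and the sample size are unaffected. No view is taken on which clinical rule is right.

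**What to change.** 1. Keep *adherent/non-adherent* for the GesEPOC measure. Relabel the Table 5 row and the response of Tables 25-27 as *ICS use without moderate/severe exacerbation in the previous year*.
2. Reconcile the premise in SAP 16.1.3.2 with 7.2.11 and 7.2.14, without ruling on the clinical question, and write *moderate/severe* into 16.1.3.2.
3. State one cohort and one denominator for this measure in 16.1.3 and Table 5, including who fills the *Adherent* row.
4. Remove the previous-year moderate/severe and severe exacerbation rows from the Table 25 regressions. Also remove the covariate for the number of exacerbations in the previous year if it counts moderate/severe events only. If *Type of ICS* stays, show it as descriptive and not as a model term.
5. Add a cross-tabulation of the two flags, which will show how often they disagree.

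The cost is SAP wording, a few table labels and rows, and one small table. Both flags are already derived for Tables 5 and 38, so no new data are needed.

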7. RATIONALE AND BACKGROUND

Chronic obstructive pulmonary disease (COPD) is essentially characterized by chronic airflow limitation that is irreversible and mainly associated with tobacco smoke. It is an underdiagnosed disease with high morbidity and mortality and is a very significant public health problem.

COPD is a complex disease with a very heterogeneous clinical presentation. Within what we know as COPD, different phenotypes can be defined that have clinical, prognostic and therapeutic repercussions.

GesEPOC guidelines identify four clinical phenotypes with differential treatment: non-exacerbator, mixed COPD-asthma (ACOS), exacerbator with emphysema and exacerbator with chronic bronchitis. Exacerbation is defined as an acute episode of clinical instability that occurs in the natural course of the disease and is characterized by a sustained deterioration of respiratory symptoms that goes beyond their daily variations. The main symptoms referred to are worsening of the dyspnoea, cough, increased volume and / or changes in the colour of the sputum [\(1\)](#).

Different clinical practice guidelines [\(2\)](#) recognize the usefulness of using inhaled corticosteroid (ICS) in patients who present frequent exacerbations despite optimal bronchodilator treatment, and their use associated with long-acting bronchodilators (LABD) produces a significant decrease in the number of exacerbations and an improved quality of life, even though they have not been shown to have a beneficial effect on mortality [\(3\)](#). However, clinical evidence has showed a higher prevalence and incidence of side effects when ICS is long-term used (such as pneumonias) [\(2\)](#).

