According to the new GOLD 2017 report [\(2\)](#) for patients with 0-1 exacerbations (not leading to hospital admission – group A/B) treatment with ICS is not recommended and for patients with ≥ 2 exacerbations or ≥ 1 exacerbation leading to hospital admission (group C/D) the preferred option is Long acting bronchodilation. It is known that almost 2/3 of the COPD patients are non-exacerbators; in these patients, an inhaled corticosteroids (ICS) therapy is not recommended and despite of this, 61% of these patients are being treated with ICS [\(4\)](#). Additionally, a Spanish consensus in the use of ICS in COPD patients recommends that the ICS therapy should be withdrawn in those patients without evidence of exacerbations in the previous two years [\(5\)](#). However there are discrepancies between guidelines and real-life practice, as ICS are still being overused.

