9.3.3 Covariates

Table 9.3.3:1 Covariates related to patient profile

	Data from Medical Charts	Data Measured at Study Visit
Age, gender, ethnicity.	X	
Height & weight (BMI auto-calculated) *	X	
Smoking history.	X	
Pulmonary function test - Spirometry # *	X	
Bronchodilator test # * (FEV ₁ increase, absolute values).	X	
Episodes of wheezing in exacerbations.	X	
COPD diagnosis (year)	X	

History of asthma (yes/no) and year of diagnose	X	
History of atopy (yes/no).	X	
Blood Eosinophilia (number of eosinophils and %) *	X	
Immunoglobulin E (Ig E) *	X	
Current COPD treatment (including ICS: start and stop dates, dose, reason) §	X	
History and details of Exacerbations (last 2 years).	X	
History of antibiotics and oral corticosteroids for COPD	X	
Comorbidities (COTE index)	X	
Concomitant medication.	X	
COPD GesEPOC 2017 phenotypes	X	
GOLD 2017 spirometric classifications (1, 2, 3, 4).	Auto-calculated	
GOLD 2017 patient groups (A, B, C, D).	Auto-calculated	
BODEx (BMI / % FEV ₁ / mMRC / severe Exacerbations)	Auto-calculated	
Breathlessness based on mMRC score.		X
QoL: CAT - COPD Assessment Test		X

* Last measure available

available in medical charts <12 months

§ Not including possible changes or new prescriptions done at study visit

The covariates will also be included as independent variables for multivariable analysis: COPD phenotypes, GOLD group, BODEx index, mMRC score and CAT – COPD Assessment Test.

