16.1.3.1 Current treatment with ICS

Main variable will be presented according to the presence or not of moderate/severe exacerbations in the previous 365 days.

The use of ICS will be analyzed using number of patients in each category and percentages (absolute and relative frequencies) and 95% confidence intervals will be provided based on Wald's (Normal Approximation) method for each group. Percentages will be compared using Chi-Square test or Fisher's Exact test.

Logistic regression will be used to assess the independent contribution of clinical and demographic factors to the estimation of the proportion of patients with COPD who use ICS inadequately. First, univariate and second, multiple logistic regression (MLR) methods will be used to investigate the impact of the following explanatory covariates (patient and disease characteristics) on ICS use.

Potential covariates are:

- Age
- gender
- Smoking history
- Number of exacerbations in the previous year.
- History of asthma (yes/no)
- History of atopy (yes/no)
- COTE index
- COPD GesEPOC 2017 phenotype

Document: \\bcnfs02\general\Hdmgener\MEDICAL AFFAIRS 28.02.2017 actualizada\8. SRO ESTUDIOS\RESPIRATORIO\1237-0070 NIS OPTI\11 - Clinical Trial Report\SAP\SAP - V 1.0\SAP OPTI version1.0 29052019.docx

Author:

Version Number: 1.0

Version Date: [29MAY2019]

Template No.: RWI_TP_BIOS0013 Revision 1

Reference: RWI_WI_BIOS0015

Effective Date: 15Jun2018

Copyright © 2018 All rights reserved. The contents of this document are confidential and proprietary to Holdings Inc. and its subsidiaries. Unauthorized use, disclosure or reproduction is strictly prohibited.

- GOLD 2019 spirometric classifications (1, 2,3, 4)
- GOLD 2019 patient groups (A, B, C, D)
- mMRC score
- CAT - COPD Assessment Test

Backward selection procedures will be applied to generate the final MLR models which consider only covariates in the selection procedure with a p-value <0.1 in the corresponding univariate logistic regression analysis, using inadequate ICS use (yes/no) as response variable. A p-value <0.05 will be used for the covariates to stay in the model in a backward elimination step. Continuous variables can be replaced by categorical variables. Parameters estimated, exp(B) and C95% Wald Confidence Limits for OR will be presented.

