COPD GesEPOC 2017 phenotypes	non-exacerbator, mixed COPD - asthma syndrome (ACOS), exacerbator with emphysema exacerbator with chronic bronchitis		(ref)	
GOLD 2019 spirometric classification	Gold 1 – Mild Gold 2 – Moderate Gold 3 – Severe Gold 4 – Very severe		(ref)	
GOLD 2019 patient groups (A, B, C, D)	Patient A Patient B Patient C Patient D		(ref)	
CAT score (cat)	CAT <10: Low impact of COPD. CAT ≥10: Medium / high impact of COPD		(ref)	
mMRC score	Grade 0 Grade 1 Grade 2 Grade 3 Grade 4		(ref)	
Number of eosinophils (%)	<2% ≥ 2%		(ref)	

Document: \\bcnfs02\general\Hdmgener\MEDICAL AFFAIRS 28.02.2017 actualizada\8. SRO ESTUDIOS\RESPIRATORIO\1237-0070 NIS OPTI\11 - Clinical Trial Report\SAP\SAP - V 1.0\SAP OPTI version1.0 29052019.docx

Author:

Version Number: 1.0

Version Date: [29MAY2019]

Template No.: RWI_TP_BIOS0013 Revision 1

Reference: RWI_WI_BIOS0015

Effective Date: 15Jun2018

Copyright © 2018 All rights reserved. The contents of this document are confidential and proprietary to Holdings Inc. and its subsidiaries. Unauthorized use, disclosure or reproduction is strictly prohibited.

Variable	Category	Inadequate use of ICS	Odds-Ratio (OR)	p-value
Inmunoglobulin E (UI/ml)	<= 100 UI/ml >100 UI/ml		(ref)	
Presence of exacerbations in previous 2 years	None 1-2 exacerbations 3-4 exacerbations 5+ exacerbations		(ref)	
Presence of moderate/severe exacerbations in previous 2 years	None 1-2 moderate/severe exacerbations 3-4 moderate/severe exacerbations 5+ moderate/severe exacerbations		(ref)	
Presence of severe exacerbations in previous 2 years	None 1-2 severe exacerbations 3-4 severe exacerbations 5+ severe exacerbations		(ref)	
Presence of exacerbations in previous year	None 1-2 exacerbations 3-4 exacerbations 5+ exacerbations		(ref)	
Presence of moderate/severe exacerbations in previous year	None 1-2 moderate/severe exacerbations 3-4 moderate/severe exacerbations 5+ moderate/severe exacerbations		(ref)	
Presence of severe exacerbations in previous year	None 1-2 severe exacerbations 3-4 severe exacerbations 5+ severe exacerbations		(ref)	
Antibiotics for COPD exacerbations	No Yes		(ref)	
Oral corticosteroids for COPD exacerbations	No Yes		(ref)	
Type of ICS	ICS alone LABA + ICS LABA + LAMA + ICS			

Inadequate use of ICS: use of ICS without moderate/severe exacerbations in the previous year in patients.

Table 26. Multivariate logistic regression model of inadequate use of ICS (use of ICS without moderate/severe exacerbations in the previous year)

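### One exacerbation-free year in a current ICS user is labelled inadequate use, although it does not show that ICS was not required

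*SAP*

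**What the plan says.** The protocol's primary outcome (9.3.2.1) is neutral: the share of current ICS users without a moderate/severe exacerbation in the prior year. Protocol 9.7.2 mentions inadequate ICS use as a possible regression outcome but does not define it.

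The SAP supplies a definition.

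- Section 16.1.3.2 makes inadequate use part of the main analysis: "This analysis will be presented only for patients without exacerbations in the previous year". The reason given is that "only patients without exacerbations can receive ICS without requiring it, which is, making an inappropriate use of the treatment".
- The footnote to Table 25 (SAP 20.3.1) reads "Inadequate use of ICS: use of ICS without moderate/severe exacerbations in the previous year in patients". The titles of Tables 26 and 27 repeat the definition.
- Table 5 (SAP 20.1) describes non-adherent patients as "Inadequate use of ICS (use of ICS in patients without moderate/severe exacerbations in the previous year".
- The window is one year (SAP 16.1.3.1): "Main variable will be presented according to the presence or not of moderate/severe exacerbations in the previous 365 days".
- Current ICS (SAP 16.1.1) needs only a start before the visit and treatment that is ongoing or stopped on the visit day. There is no minimum duration and no condition on why ICS was started.

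Protocol section 7 says that ICS with long-acting bronchodilators "produces a significant decrease in the number of exacerbations and an improved quality of life". It also cites a Spanish consensus that "ICS therapy should be withdrawn in those patients without evidence of exacerbations in the previous two years". Protocol Table 9.3.3:1 collects "Current COPD treatment (including ICS: start and stop dates, dose, reason", along with the two-year exacerbation history. None of these enters the label.

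**The concern.** The label reads a past event-free year as evidence about need. For someone who has been on ICS throughout that year, no events is what a patient who never needed ICS would show, and also what a patient who responds to it would show. The definition cannot separate the two, and the protocol's own background says that the second kind of patient exists.

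The window adds a second difficulty. Take a patient who had two treated exacerbations 19 and 20 months before the visit, started ICS 18 months before it, and has had no event since. The SAP counts this patient as an inadequate user. The consensus cited in the protocol speaks of two event-free years, which this patient does not have. Table 25 itself cross-tabulates inadequate use by moderate/severe exacerbations over two years, with categories up to five or more, so the SAP allows for such patients.

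At stake is the meaning of a percentage and of a regression response that both sit in the main analysis. The odds ratios in Tables 25–27 may partly describe who stays event-free on ICS rather than who receives it without need.

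**Working it through.** **1. The plan's own figures (Protocol 9.5, SAP 4.2).** Inputs: 66% non-exacerbators, 61% of them on ICS, n = 900.

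- 0.66 × 0.61 = 0.4026, which the plan rounds to 40%. 0.4026 × 900 = 362 patients.
- Wald 95% interval at 40%: 0.40 ± 1.96 × √(0.40 × 0.60 / 900) = 0.40 ± 0.032, i.e. 36.8% to 43.2%. This reproduces.
- 900 / 0.90 = 1,000. This reproduces.

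**2. Second-year events among the 362.** The documents give no two-year event-free rate, so the following is an assumed range. Counts are fixed to 66% event-free in one year, and ICS use is taken as unrelated to second-year status among those event-free in the last year. For a negative binomial with dispersion d, the yearly mean is m = (0.66^(−d) − 1)/d, and the two-year event-free share is (1 + 2dm)^(−1/d). For Poisson the two-year share is 0.66² = 0.4356. The share of the one-year group with a second-year event is 1 − (two-year share)/0.66.

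| Model | Event-free over two years | Second-year event, share of the 362 | Patients | All-patient figure, two-year window |
|---|---|---|---|---|
| Poisson | 43.6% | 34.0% | 123 | 26.6% |
| d = 1 | 49.3% | 25.4% | 92 | 30.0% |
| d = 2 | 52.8% | 20.1% | 73 | 32.2% |
| d = 4 | 56.9% | 13.8% | 50 | 34.7% |
| Status never changes | 66.0% | 0% | 0 | 40.3% |

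Except in the last row, the shift is 5.6 to 13.7 points, against a planned half-width of 3.2. In the Poisson case the 95% interval at n = 900 would be 23.7% to 29.5%.

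**3. The denominator.** Step 2 uses all evaluable patients, as Table 5 does. Section 16.1.3.2 uses only event-free patients: 0.66 × 900 = 594, of whom 0.61 × 594 = 362, or 61%. If that cohort is itself redefined by two years, the Poisson case gives 0.4356 × 900 = 392 patients and 0.61 × 392 = 239 on ICS, again 61%. Under this model the cohort percentage does not move, although different patients carry the label.

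**4. Treatment response.** The documents give no size for the ICS effect, so this too is assumed. If ICS multiplies a constant event rate by r, and a share q of fully exposed users is event-free over a year, the fraction of those event-free users who would have had an event without ICS is 1 − q^(1/r − 1).

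- q = 0.66: 4.5% at r = 0.9 (16 of 362), 9.9% at r = 0.8 (36), 16.3% at r = 0.7 (59).
- q from 0.50 to 0.80, r from 0.9 to 0.7: 2.5% to 25.7%.

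The patient counts treat all 362 as exposed for the whole year.

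**5. The competing criteria side by side.**

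- One-year label (Tables 5, 25–27): on ICS, no moderate/severe event in 365 days.
- Consensus (Protocol 7): two years without exacerbations, stated as a condition for withdrawing ICS.
- GOLD 2017 as reported in Protocol 7: ICS not recommended with 0–1 exacerbations not leading to admission.
- GesEPOC (SAP 7.2.11 and 7.2.14): ICS indicated only at high risk with certain phenotypes. SAP 7.2.14 also calls departures from this inadequate use.

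An event-free patient with FEV₁ below 50% and the mixed phenotype is inadequate under the first and indicated under the last. An ICS user with one moderate exacerbation and otherwise low risk is not counted by the first, but falls outside the ICS recommendation under GOLD as reported and under SAP 7.2.14.

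**The case against.** The strongest reply is that much of the needed information is already planned. The primary outcome is neutrally worded. Two-year status has its own secondary analysis with confidence intervals (SAP 16.2.1). Table 16 reports time on each ICS, and guideline adherence is reported separately (SAP 16.2.5, Table 38). P-values are descriptive (SAP 8.2), and Protocol 9.9 disclaims causal conclusions. All of this is true, but none of it changes the label or the regression response, and Protocol 9.9 does not mention treatment response.

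Several stronger readings are tempting and do not hold.

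- A reader might infer that the label always overstates overuse. Treatment response and second-year events do inflate the count, but the label also leaves out ICS users with one non-hospitalised exacerbation, whom two of the documents' other criteria would include.
- A reader might infer that two years is the correct criterion. The protocol cites it for withdrawal, alongside other criteria, and choosing among them is not a statistical matter. Nor would a longer window cure the response problem: two event-free years on ICS do not show lack of need either.
- A reader might take the whole look-back year as on-treatment time. SAP 16.1.1 sets no minimum duration, so the response argument applies only to users exposed for much of the year. The second-year argument does not depend on exposure.

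**Conclusion.** The point stands in a limited form. One year without a moderate/severe exacerbation in a current ICS user does not establish that ICS was not required, and the SAP builds a main-analysis label and regression response on the premise that it does. The documents also hold criteria that disagree with that label, so the net direction of misclassification is not known.

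The size rests on assumptions. Across the models tried, 0% to 34% of about 362 labelled patients had a second-year event, which would put the all-patient figure at about 27% to 40% under a two-year window. If ICS was started because of second-year events, the share would be larger than modelled, and the 61% within the event-free cohort would fall as well. With no such link the 61% need not move.

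A reader might go further and infer that the primary outcome is invalid or that the study is built to show overuse. The documents support neither: the outcome in Protocol 9.3.2.1 makes no claim about need, the stated primary objective is a patient profile, and the sample-size arithmetic is sound.

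**What to change.** 1. In SAP 16.1.3.2 and Tables 5 and 25–27, rename the variable and the regression response *on ICS, no moderate/severe exacerbation in the prior year*. Delete the sentence that justifies the cohort by lack of need. Use the same event wording throughout, since 16.1.3.2 says exacerbations where the tables say moderate/severe.
2. Reconcile the one-year label, the criteria cited in Protocol section 7 and the GesEPOC definition in SAP 7.2.14. Keep the term inadequate use for the single definition the sponsor then states.
3. Add a sensitivity analysis of the proportion and the regression with a two-year window, stating the denominator (all evaluable patients or the event-free cohort).
4. Split the one-year group by ICS start (under 12, 12–24, over 24 months before the visit) and by moderate/severe exacerbations in the second year back. Note that history before ICS is not visible for users of more than 24 months. The recorded reason may mean the reason for stopping, so check the eCRF before using it.
5. State as a limitation that absence of events on ICS does not establish lack of need.

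The data are already collected and the primary outcome is unchanged. The cost is SAP wording, the sensitivity run, one extra table and a less emphatic statement about overuse.
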